### **Setting and study population**

The study population includes pregnant women who reside in the US or Canada.

Three cohorts of women will be enrolled prospectively into the cohort study and followed for pregnancy and infant outcomes:

- Siponimod-Exposed Cohort: Pregnant women with MS exposed to siponimod during pregnancy (i.e. on or any time after the 4th day post the first day of LMP prior to conception) (N = 289)
- Disease-Matched Comparison Cohort: Pregnant women with MS not exposed to siponimod during pregnancy (N = 289)
- Healthy Comparison Cohort: Pregnant women who are neither diagnosed with MS nor with any other autoimmune disease, and not exposed to siponimod or any known teratogenic agent during pregnancy (N = 289)

The term “exposed to siponimod” is used here as synonym to “administered siponimod”.

Using the multi-product registry concept, this Mayzent-OTIS pregnancy registry (BAF312A2403), will be leveraged for the Kesimpta-OTIS pregnancy registry sub-study (OMB157G2403). Considering the identical population (inclusion/exclusion criteria) and design, the Kesimpta-OTIS sub-study will use the contemporaneous Mayzent-OTIS pregnancy registry comparator cohorts.

The ‘Disease-Matched Comparison Cohort’ and the ‘Healthy Comparison Cohort’ will be common between this study and the Kesimpta-OTIS pregnancy registry sub-study (OMB157G2403) study. The first 125 pregnancies in the two comparison groups from the time of the Kesimpta protocol (OMB157G2403) approval will be eligible for inclusion in both studies (i.e., the current study and the Kesimpta-OTIS pregnancy registry sub-study).

Up to an additional 50 women will be enrolled in an exposure series group. This is a group of women with exposure to siponimod during pregnancy, but who do not meet eligibility criteria for the siponimod-exposed cohort group (e.g. retrospective cases would be enrolled in the exposure series group).

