#### **Cohort 1: Siponimod-Exposed Cohort**

1. Women who have enrolled in the siponimod cohort study with a previous pregnancy
2. Women who have used siponimod for an indication other than a currently approved indication
3. Women with exposure to any of the following medications within 5 half-lives prior to conception:
  - Cladribine (Mavenclad)
    - Based on the US label, animal studies indicate that there is positive evidence of teratogenicity for Cladribine
  - All other S1P modulators including fingolimod (Gilenya), ozanimod, etc.
    - S1P modulators are in the same class of drug as siponimod
  - Teriflunomide (Aubagio)
    - The teratogenicity of teriflunomide is unknown and currently under investigation
  - Other anti-CD20 monoclonal antibody: same class as Kesimpta
  - New medications (marketed after 2020) indicated for the treatment of MS will be evaluated for inclusion/exclusion criteria as the study progresses.
4. Retrospective enrollment after the outcome of pregnancy is known (i.e. the pregnancy has ended prior to enrollment)
5. Results of a diagnostic test are positive for a major structural defect prior to enrollment ([Section 7.7.2.3](#)). However, women who have had any normal or abnormal prenatal screening or diagnostic test prior to enrollment are eligible as long as the test result does not indicate a major structural defect.

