### **Cohort 2: Disease-Matched Comparison Cohort (Comparison Group 1):**

1. Exposure to siponimod any time from the 4th day post the first day of LMP prior to conception up to and including end of pregnancy
2. Women with exposure to any of the following medications within 5 half-lives of conception:
  - Cladribine (Mavenclad)
  - SIP modulators
  - Teriflunomide (Aubagio)
  - Anti CD-20 monoclonal antibody

New medications (marketed after 2020) indicated for the treatment of MS will be evaluated for inclusion/exclusion criteria as the study progresses.

3. Women who have enrolled in the siponimod cohort or OMB157G2403 Kesimpta cohort with a previous pregnancy
4. Retrospective enrollment after the outcome of pregnancy is known (i.e. the pregnancy has ended prior to enrollment)
5. Results of a diagnostic test are positive for a major structural defect prior to enrollment. However, women who have had any normal or abnormal prenatal screening or diagnostic test prior to enrollment are eligible as long as the test result does not indicate a major structural defect.

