### **Cohort 3: Healthy Comparison Cohort (Comparison Group 2):**

1. Exposure to Kesimpta 166 days before or to siponimod any time from the 4th day post first day of LMP prior to conception up to and including end of pregnancy
2. Women who have a diagnosis of a MS or a siponimod approved indication
3. Women who have a current diagnosis of any autoimmune disease
4. Women who have first contact with the project after prenatal diagnosis of any major structural defect
5. Women who have enrolled in the siponimod cohort or Kesimpta cohort study with a previous pregnancy
6. Women treated with Mayzent or Kesimpta for non-MS indication
7. Retrospective enrollment after the outcome of pregnancy is known (i.e. the pregnancy has ended prior to enrollment)
8. Results of a diagnostic test are positive for a major structural defect prior to enrollment. However, women who have had any normal or abnormal prenatal screening or diagnostic test prior to enrollment are eligible as long as the test result does not indicate a major structural defect.
9. Women exposed to a known human teratogen during pregnancy as confirmed by the OTIS Research Center

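### The anti-CD20 exclusion is worded differently in the two cohorts of the primary comparison, and read literally it leaves Kesimpta permitted in the siponimod cohort but barred from the disease-matched comparator

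*Protocol*

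**What the plan says.** Section 7.2.2.2 of the protocol lists drug exclusions separately for each cohort.

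- **Cohort 1 (siponimod-exposed).** The list opens with "Women with exposure to any of the following medications within 5 half-lives prior to conception". It includes "All other S1P modulators including fingolimod (Gilenya), ozanimod, etc" and, further down, "Other anti-CD20 monoclonal antibody: same class as Kesimpta". The only previous-enrolment rule is "Women who have enrolled in the siponimod cohort study with a previous pregnancy". No other exclusion for this cohort mentions Kesimpta.
- **Cohort 2 (disease-matched).** The list opens with "Women with exposure to any of the following medications within 5 half-lives of conception" and includes "Anti CD-20 monoclonal antibody", with no qualifier. Its previous-enrolment rule names the Kesimpta cohort as well as the siponimod cohort.
- **Cohort 3 (healthy).** Kesimpta is named, with a fixed look-back: "Exposure to Kesimpta 166 days before or to siponimod any time from the" fourth day after LMP. Women with MS, and women treated with Kesimpta for another indication, are excluded separately.

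Section 7.7.3.1.1 makes Cohort 1 versus Cohort 2 the primary comparison. It places all potential confounders in the propensity score, used through inverse probability weighting. Table 7-1 lists MS treatment history as a confounder. The Abstract and section 7.2 make both comparison cohorts common to this study and the Kesimpta registry, with the first 125 pregnancies in each counting in both.

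**The concern.** The protocol treats anti-CD20 exposure near conception as a reason to exclude a woman with MS. That protects the primary comparison only if the exclusion works the same way on both sides, and the two lists differ in two respects.

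First, the drug. The Cohort 1 line itself places Kesimpta in the anti-CD20 class, so the unqualified Cohort 2 line bars it. The Cohort 1 line bars the other members of the class, and the only drug the word can set apart is Kesimpta.

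Second, the time window. The Cohort 1 window runs up to conception and is silent on use after it. The Cohort 2 window is centred on conception and can be read as covering both sides.

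A woman who moved between Kesimpta and siponimod around conception could then enter the exposed cohort, while the same Kesimpta exposure would keep a woman out of the comparator. If Kesimpta affected the risk of major defects, the contrast would attribute that effect to siponimod.

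**Working it through.** **Step 1: what the Cohort 1 line covers.** The S1P line in the same list shows how the drafting works: there, other means other than the study drug, siponimod. Siponimod is an S1P modulator (section 5), not an anti-CD20 antibody, so in the anti-CD20 line the word cannot refer to the study drug. The one drug named in that line is Kesimpta. The literal result is that the class is excluded except Kesimpta.

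**Step 2: does another Cohort 1 rule close the gap?** No. The remaining items concern previous enrolment in the siponimod cohort, indication, retrospective enrolment and a positive diagnostic test.

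**Step 3: the two cohorts side by side, read literally.**

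| | Cohort 1 | Cohort 2 |
|---|---|---|
| Kesimpta | not covered | excluded |
| Other anti-CD20 antibodies | excluded | excluded |
| Window | 5 half-lives before conception | 5 half-lives of conception |
| Use after conception | not mentioned | arguably covered |

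The window difference sits in the opening line of each list, so it applies to every drug listed and not only to anti-CD20 antibodies.

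**Step 4: can the planned adjustment repair it?** Not for this exposure. If Cohort 2 contains no woman with Kesimpta near conception, a woman with that exposure is in Cohort 1 with probability 1. Weighting has no comparable Cohort 2 woman to up-weight. Listing treatment history as a confounder does not supply one.

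**Step 5: scale.** The protocol gives neither the share of Cohort 1 exposed to Kesimpta (f) nor Kesimpta's risk ratio for major defects (k), so both are assumed. With no siponimod effect and no such exposure in Cohort 2, the apparent siponimod risk ratio is

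[p(1 − f) + p·f·k] / p = 1 + f(k − 1), where p is the baseline risk.

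| f | k = 2 | k = 3 |
|---|---|---|
| 0.02 | 1.02 | 1.04 |
| 0.10 | 1.10 | 1.20 |
| 0.20 | 1.20 | 1.40 |

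If Kesimpta were protective, the bias would run the other way: f = 0.10 and k = 0.8 give 0.98.

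With 231 live-birth pregnancies per cohort and a 3% baseline (section 7.5.1), the expected count is 231 × 0.03 = 6.9. At an apparent ratio of 1.20 it is 231 × 0.036 = 8.3. In the extreme cell (f = 0.20, k = 3) the two-sided Fisher exact test rejects in 6.5% of studies with no siponimod effect, against 2.4% without contamination. Fisher's test is the one behind Table 7-4, not the weighted analysis, so these percentages show scale only.

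**The case against.** The strongest reply is that the Cohort 1 line does not say Kesimpta is allowed. It can be read as excluding the whole class, with Kesimpta named to identify the class. The wording would fit a Kesimpta-exposed cohort, so a carry-over from the companion registry is plausible, though that is an inference. This stands, and it limits how firmly the defect can be stated. It does not remove it: the two readings give opposite answers for the same woman, and enrolment staff need one.

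The second reply is that the bias is small. It also stands. At 1.02 to 1.20 it is well below the detectable ratio of 3.0 in Table 7-4, and the inputs are assumptions.

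Three stronger readings are tempting, and the protocol does not support them.

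- *That three different Kesimpta rules confound the primary comparison.* Cohort 3 is not part of that comparison. Its 166-day rule bears only on the secondary comparison and on the possible pooling of comparison groups in section 7.5.1.
- *That Cohort 2 admits women inside the 166-day window and so pulls the siponimod risk ratio toward 1.* Five half-lives reach 166 days only if the half-life is at least 166/5 = 33.2 days, or (166 + 14)/5 = 36.0 days if the 166 days run from LMP and conception is LMP + 14. The protocol gives no half-life, and the anchor of the 166 days is unclear. Under first-order elimination, a woman past five half-lives would retain at most 0.5^5, about 3%, of the drug, so giving her the full assumed effect is not justified.
- *That the claim of harmonised criteria is broken.* The Abstract's "Considering the identical population (inclusion/exclusion criteria) and design" and the amendment table in section 3 concern alignment between the two registries. They do not promise the same drug window in Cohorts 1, 2 and 3.

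**Conclusion.** The point holds as an inconsistency in operative eligibility text, inside the primary comparison. Cohorts 1 and 2 differ in how the anti-CD20 exclusion names its drugs and in how its window is placed around conception. On the literal reading this creates an exposure that only the siponimod cohort can contain, which the propensity score cannot balance.

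The size is uncertain and probably modest: a null risk ratio of 1.02 to 1.20 for f of 2-10% and k of 2-3. It rests on the literal reading, on no Kesimpta exposure near conception in Cohort 2, and on inputs the protocol does not supply. A reader might infer that Kesimpta users are knowingly admitted to Cohort 1. The text is too ambiguous to support that. The correction is worth making because it is cheap and concerns the primary contrast, not because a large bias has been shown.

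**What to change.** Reconcile the Cohort 1 and Cohort 2 lists in section 7.2.2.2:

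1. State the anti-CD20 exclusion in the same words in both cohorts, and say explicitly whether Kesimpta is covered.
2. State the window in the same terms in both: where it starts, the date it is anchored to, and whether it extends into pregnancy. This also settles the difference for the other drugs on the lists.
3. Reconcile this with the separately worded Kesimpta window in Cohort 3, for the secondary comparison and any pooling, and make the anchor of the 166 days clear.
4. Keep the shared comparator criteria aligned with the Kesimpta registry (OMB157G2403).
5. Check medication histories already collected and apply the reconciled rule before the final analysis. Siponimod-exposed women excluded by it can be followed in the exposure series of section 7.2.2.3.

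The protocol does not show which window is right, and none is proposed here.

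The cost is a short amendment, coordination with the Kesimpta registry, and a review of existing records. A few women may leave the cohort analysis.

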### **7.4.3.2 Interim interview I and II (~20 and 32 weeks' gestation)**

Following the initial intake interview, participants will be sent a pregnancy exposure diary on which they will be asked to record any additional exposures (medications, vaccinations, vitamins, etc.) or events as the pregnancy progresses. Along with the pregnancy exposure diary, each woman will be sent a copy of the written informed consent document, and a research HIPAA compliant obstetric medical record release form.

Women who have enrolled in the study prior to 18 weeks post-LMP will be interviewed by telephone at 20-22 weeks post-LMP, 32-34 weeks post-LMP and within 0-6 weeks after the expected due date. Women who have enrolled between 18 and 20 weeks post-LMP will be interviewed at 32-34 weeks post-LMP and within 0-6 weeks after the expected due date.

Women who enrolled after 20 weeks post LMP and before 30 weeks post-LMP will be interviewed at 32-34 weeks post-LMP and within 0-6 weeks after the expected due date. Women who have enrolled after 30 weeks post-LMP will be interviewed within 0-6 weeks after the expected due date (See [Table 7-2](#)).

The purpose of these interviews will be to update records of pregnancy exposures and results of prenatal tests, to remind women to maintain the pregnancy exposure diary, to update phone number and address information, and to determine if the pregnancy has ended prior to the expected due date.

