**Table 7-2 Timing of Cohort Enrollment, Interviews, Examinations, and Medical Records**

	Anytime In Pregnancy	20-22 Weeks' Gestation b	32-34 Weeks' Gestation c	0-6 Weeks Post-Delivery	0-12 Months Post-Delivery	1 Year Post-Delivery
Referral a	√					
Enrollment and Consent a	√					

Enrollment Interview a	√					
Interim Interview I		√				
Interim Interview II			√			
Pregnancy Outcome Interview and Request for Medical Records				√		
Medical Record Review					√	
Dysmorphology Examination					√	
Developmental Screening / ASQ						√
Pediatric 1-Year Medical Records Request and Review						√

aParticipants may enroll in the study anytime during pregnancy

bIf subject is enrolled and Intake Interview is conducted after 18 weeks' gestation, only one interim interview will be conducted during pregnancy at 32-34 weeks gestation

cIf subject is enrolled and Intake Interview is conducted at 30 weeks' gestation or after, no Interim Interview will be collected

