#### **7.7.2.4 Outcome classification for secondary outcomes**

- ***Spontaneous abortion:*** spontaneous abortion/miscarriage is defined as non-deliberate fetal death which occurs prior to less than 20.0 weeks post-LMP.
- ***Analysis subset:*** the analysis subset for the secondary outcome of spontaneous abortion will be restricted in Cohort 1 to those who were exposed to any dose from

the 4th day post first day of LMP prior to conception to 20 weeks' gestation and enrolled prior to 20 weeks' gestation. The analysis subset for cohorts 2 and 3 will be restricted to those who enrolled prior to 20 weeks' gestation.

- **Stillbirth:** stillbirth is defined as non-deliberate fetal death anytime in gestation at or after 20 weeks post-LMP.
- **Elective termination:** elective termination/abortion is defined as deliberate termination of pregnancy at any time in gestation. Reasons for elective abortions are captured and are classified as due to medical reasons or social reasons.
- **Premature delivery:** premature delivery is defined as live birth prior to 37.0 weeks gestation as counted from LMP (or calculated from first-trimester ultrasound-derived due date if last menstrual period uncertain or more than 1 week discrepant). Elective caesarian deliveries or inductions prior to 37.0 completed weeks will be considered separately.
- **Preeclampsia / eclampsia:** preeclampsia or eclampsia reported by maternal interview with confirmation in medical record or report by medical record only is captured.
- **Small for gestational age:** small for gestational age is defined as birth size (weight, length or head circumference) less than or equal to the 10th centile for sex and gestational age using standard pediatric CDC growth curves for full term or preterm infants (CDC, 2000; Olsen et al., 2010).
- **Minor structural defects:** a minor structural defect is defined as a defect which has neither cosmetic nor functional significance to the child (e.g., complete 2,3 syndactyly of the toes). Minor structural defects will be identified only through the study dysmorphology examination for live born infants using the study-specific checklist.

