### **7.7.3.1.2 Analyses of secondary outcomes**

The analysis of spontaneous abortion (SAB) and stillbirth: Only those subjects who are enrolled prior to 20 weeks of gestation are eligible for the analysis of SAB. Since they are not followed from gestational age zero, survival analysis methods will be used to handle left truncation, as well as right-censoring when a subject is lost-to-follow-up prior to 20 weeks' gestation. Left-truncated Kaplan-Meier estimate at 20 weeks' gestation will be used to estimate the SAB rate in each of the cohorts (Tsai et al, 1987). The Cox proportional hazards regression models incorporating left truncation will be used to estimate the hazard ratio (HR) of different cohorts, as well as to obtain the 95% CIs. Stillbirth will be analyzed in a similar fashion. To account for potential confounding, PS methods described above will be applied, where regression adjustment will be used with the Cox model to obtain the adjusted HR.

The analysis of premature delivery: Only those subjects who are enrolled prior to 37 weeks of gestation are eligible for the analysis of premature delivery. These data will be analyzed similarly to SAB, as described above, using survival analysis methods to handle possible right-censoring.

The following will be considered binary endpoints: preeclampsia/eclampsia, small for gestational age (SGA) at birth in weight, height and head circumference, respectively, and growth deficiency at about one year of age in weight, height and head circumference respectively. The analysis of each of these outcomes will be similar to the analysis of the primary outcome, based on all pregnancies resulting in live born infants excluding twins or higher order multiples.

Multiple births will be included in the analyses of minor structural defects, ASQ, and serious or opportunistic infections. These outcome variables will thus likely contain correlated data due to twins or higher order multiples, and the generalized estimating equations (GEE) approach will be used (Liang and Zeger, 1986, Diggle et al, 2002).

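### Pre-eclampsia diagnosed before enrolment counts as an event, because neither eligibility nor the analysis set requires women to be free of it at entry; for pregnancy losses the dating rule is left open

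*Protocol*

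**What the plan says.** **Eligibility (Protocol 7.2.2.2).** Cohort 1 excludes "Retrospective enrollment after the outcome of pregnancy is known (i.e. the pregnancy has ended prior to enrollment", so an outcome is known only once the pregnancy is over. Women with an earlier abnormal screening or diagnostic test "are eligible as long as the test result does not indicate a major structural defect". Cohorts 2 and 3 carry the same two rules.

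**Time of entry.** Table 7-2 notes that "Participants may enroll in the study anytime during pregnancy". Late entry is foreseen in section 7.4.3.2: "Women who have enrolled after 30 weeks post-LMP will be interviewed within 0-6 weeks after the expected due date".

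**Pre-eclampsia.** Section 7.7.2.4 sets the definition: "preeclampsia or eclampsia reported by maternal interview with confirmation in medical record or report by medical record only is captured". It has no condition on when the condition arose. Section 7.7.3.1.2 treats it as a binary endpoint, analysed like the primary outcome and "based on all pregnancies resulting in live born infants excluding twins or higher order multiples".

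**Spontaneous abortion (SAB), stillbirth and premature delivery.** For SAB, "Only those subjects who are enrolled prior to 20 weeks of gestation are eligible for the analysis of SAB", and "survival analysis methods will be used to handle left truncation, as well as right-censoring". Stillbirth is handled similarly, and premature delivery is limited to women enrolled before 37 weeks. Table 7-1 defines the SAB event as embryonic or fetal death. Under section 7.7.3.2, an unknown SAB date is drawn uniformly from a window of possible times.

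**The concern.** A prospective comparison of incidence should count events that arise after a woman comes under observation. If a woman can join because, or after, the event has happened, her case is prevalent at entry. It then enters the numerator through the route by which she was recruited, not through risk observed in follow-up.

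The plan guards against this for major defects, through the exclusion criterion and through the prior-testing sensitivity analyses in section 7.7.3.1.1. Those analyses cover the primary outcome only. SAB and premature delivery have entry limits and survival methods. Pre-eclampsia has neither, although it arises later in pregnancy and enrolment stays open beyond 30 weeks.

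At stake is the pre-eclampsia risk ratio. Prevalent cases in one cohort can create or hide a difference; equal shares in both cohorts pull a real difference towards 1.

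**Working it through.** **Step 1. Can an already-diagnosed woman enter and be counted?**

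| Outcome | Entry limit | Event-free at entry required? | Method |
|---|---|---|---|
| SAB | before 20 weeks | implied by left truncation, if the loss is dated at death | left-truncated Kaplan-Meier and Cox |
| Stillbirth | none stated separately | as for SAB | similar to SAB |
| Premature delivery | before 37 weeks | yes, since she is still pregnant at entry | survival methods |
| Pre-eclampsia/eclampsia | none | no | binary, singleton live births |

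No exclusion criterion in any cohort mentions pre-eclampsia. A woman diagnosed at 31 weeks who enrols at 32 weeks and has a singleton live birth meets every stated condition and counts as an event.

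**Step 2. The plan's own figure.** The power tables have no pre-eclampsia row. The nearest stated figure is SAB/stillbirth in Table 7-4: 259 per group, 10% in the comparison group, relative risk 1.9, two-sided Fisher's exact test at 0.05, 80% power. Exact enumeration at 10% versus 19% gives 0.802, so the stated figure is reproduced and is not in dispute.

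**Step 3. Illustrative size for pre-eclampsia.** Let p be the true risk after entry and q the share of a cohort already diagnosed at entry. The observed risk is q + (1 - q)p. Neither p nor q is in the protocol; I assume p = 3%, 5% or 8% and q = 0.5%, 1% or 2%. With 231 live-birth pregnancies per cohort (Table 7-4), these values of q are 1.2, 2.3 and 4.6 women.

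True risk ratio 1, already-diagnosed women in one cohort only, that cohort in the numerator. For example, at p = 5% and q = 1%: (0.01 + 0.99 x 0.05)/0.05 = 0.0595/0.05 = 1.19.

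| q | p = 3% | p = 5% | p = 8% |
|---|---|---|---|
| 0.5% | 1.16 | 1.10 | 1.06 |
| 1% | 1.32 | 1.19 | 1.12 |
| 2% | 1.65 | 1.38 | 1.23 |

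If these women are all in the comparison cohort, the ratios invert. At q = 1% they become 1/1.323 = 0.76, 1/1.19 = 0.84 and 1/1.115 = 0.90.

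True risk ratio 2, with q = 1% in both cohorts: at p = 5%, (0.01 + 0.99 x 0.10)/(0.01 + 0.99 x 0.05) = 0.109/0.0595 = 1.83. At p = 3% and 8% the results are 1.75 and 1.89.

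**Step 4. Pregnancy losses.** The SAB event is death. Under left truncation, a death dated before enrolment never enters the risk set, so the method removes it. Two routes remain by which a loss diagnosed before entry could still count:

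- The recorded date is that of expulsion. Section 7.4.3.3 collects the date and type of outcome, and no section says whether a loss is dated at death, diagnosis or expulsion.
- The date is imputed under section 7.7.3.2 and the draw falls after enrolment, even though non-viability had been documented before it.

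**The case against.** The strongest counter-argument is that this hardly matters in practice. Section 7.5.1 expects mean entry at 7-10 weeks post-LMP, and section 7.9 says that enrolment of a high proportion after 20 weeks has not been the experience in earlier studies. All cohorts are recruited through the same channels. Gestational age at enrolment, referral source and prenatal tests before enrolment are listed confounders; section 7.9 plans a sensitivity analysis by gestational age at enrolment and monitoring of entry times. The separate analysis plan could also add a subset rule.

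Most of this stands as an argument about size, and it is why the point is minor. It does not close the gap. Balancing or stratifying on when women enter does not remove a case diagnosed before entry. The protocol itself also fixes the pre-eclampsia definition and analysis population, and as written that population admits prevalent cases.

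Two stronger readings are tempting, and the documents support neither.

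- A reader might infer that women with a known non-viable pregnancy are simply counted as new SAB or stillbirth events. The event definition and left truncation point the other way, except in the two situations in Step 4. Crude sums can look alarming: at the 10% baseline, 2-5% prevalent losses in the exposed cohort only would turn a risk ratio of 1 into 1.18-1.45. But these use an assumed one-cohort share and a pooled crude ratio, whereas the plan estimates hazard ratios with delayed entry and handles stillbirth separately from SAB.
- A reader might infer that the bias must run against siponimod, because exposed women with a bad finding have more reason to call. Section 7.9 says exposed women may enrol earlier than comparators, which would leave fewer already-diagnosed cases among them. The direction is open.

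**Conclusion.** For pre-eclampsia the point holds on the text: a diagnosis made before enrolment is admitted and counted, with no at-risk restriction of the kind that SAB and premature delivery have. Its size cannot be derived from the protocol. Under the assumed 3-8% risk, 1% already diagnosed in one cohort moves a true risk ratio of 1 to 1.32-1.12, or to 0.76-0.90 if the cases are among comparators. With early mean entry the real share is probably small.

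For SAB and stillbirth the point is narrower: the method is sound for losses dated at death before entry, and only an unstated dating and imputation rule leaves room for miscounting. The primary outcome is not affected. Severity is minor.

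**What to change.** In Protocol 7.7.2.4 and 7.7.3.1.2:

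- **Pre-eclampsia/eclampsia:** restrict the comparison to women without the condition documented before the enrolment date, and list the excluded women by cohort. Add a sensitivity analysis limited to women enrolled before 20 weeks. This is useful in its own right: once prevalent cases are removed, women who enter late and event-free have less remaining time at risk.
- **SAB and stillbirth:** state that a loss whose non-viability was documented before enrolment is not an incident event and is left out of the risk set, including when its date is imputed.

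The cost is a few events removed. The intake interview already asks about current pregnancy complications (section 7.4.3.1) and obstetric records are requested. The protocol does not say that the date of a pre-eclampsia diagnosis is recorded, so one abstraction field may be needed. No new visits or contacts are required.
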